5.1.3 Safety Population

The safety population includes all patients who enrolled in the study and initiated use of Ability MyCite.

5.2 Efficacy Analysis

NA.

5.3 Safety Analysis

All safety analyses for this study will be descriptive in nature and apply only to the Abilify MyCite group. Drug-related SAEs, device-related AEs including those leading to withdrawal from Abilify MyCite, potential hepatotoxicity cases, pregnancies, pregnancy-related outcomes will be coded Medical Dictionary for Regulatory Activities (MedDRA) using and descriptively summarized by System Organ Class (SOC) and Preferred Term (PT). Pregnancies and pregnancy-related outcomes will be summarized by those occurring in female patients versus those occurring in female partners of male patients.

5.3.1 AEs

For the purpose of this study, AEs that do not meet the definition for a “serious” AE (section 4.1.1 and section 4.1.2 of the protocol) will only be collected if they are device-related (i.e., related to the device component of Abilify MyCite, including those leading to withdrawal from Abilify MyCite.)

5.3.2 SAEs

All AEs meeting the definition of drug-related SAE (section 4.1.1 of the protocol) and device-related SAE (section 4.1.2 of the protocol) will be collected.

5.3.3 Potential Hepatotoxicity Cases

Potential hepatotoxicity cases will be collected with other AEs.

5.3.4 Pregnancy

Pregnancies occurring in female patients taking Ability MyCite during the study and within 30 days of the last dose of Abilify MyCite will be collected. Additionally, pregnancies occurring in female partners of male patients taking Ability MyCite during the study and within 90 days of the last dose of Abilify MyCite will be collected. Pregnancy, perinatal, and neonatal outcomes will be collected.

6.0 CCI [REDACTED]

[REDACTED]

[REDACTED]

[REDACTED]	[REDACTED]	[REDACTED]	[REDACTED]	[REDACTED]	[REDACTED]	[REDACTED]
[REDACTED]	[REDACTED]	[REDACTED]	[REDACTED]	[REDACTED]	[REDACTED]	[REDACTED]
■	■	■	■	■	■	■

[REDACTED]

[REDACTED]	[REDACTED]	[REDACTED]	[REDACTED]	[REDACTED]	[REDACTED]	[REDACTED]
[REDACTED]	[REDACTED]	[REDACTED]	[REDACTED]	[REDACTED]	[REDACTED]	[REDACTED]

C						

[Redacted]

[Redacted]	[Redacted]	[Redacted]	[Redacted]	[Redacted]	[Redacted]	[Redacted]
[Redacted]	[Redacted]	[Redacted]	[Redacted]	[Redacted]	[Redacted]	[Redacted]

[Redacted]

[Redacted]	[Redacted]	[Redacted]	[Redacted]	[Redacted]	[Redacted]	[Redacted]
[Redacted]	[Redacted]	[Redacted]	[Redacted]	[Redacted]	[Redacted]	[Redacted]

[Redacted]

[Redacted]	[Redacted]	[Redacted]	[Redacted]	[Redacted]	[Redacted]	[Redacted]
[Redacted]	[Redacted]	[Redacted]	[Redacted]	[Redacted]	[Redacted]	[Redacted]

CCI [Redacted]

[Redacted]

[Redacted]

[Redacted]	[Redacted]	[Redacted]	[Redacted]	[Redacted]	[Redacted]	[Redacted]
[Redacted]	[Redacted]	[Redacted]	[Redacted]	[Redacted]	[Redacted]	[Redacted]
[Redacted]	[Redacted]	[Redacted]	[Redacted]	[Redacted]	[Redacted]	[Redacted]

[Redacted]

[Redacted]	[Redacted]	[Redacted]	[Redacted]
[Redacted]	[Redacted]	[Redacted]	[Redacted]

[Redacted]

[Redacted]

[Redacted]

[Redacted]

[Redacted]	[Redacted]	[Redacted]	[Redacted]	[Redacted]	[Redacted]	[Redacted]
[Redacted]	[Redacted]	[Redacted]	[Redacted]	[Redacted]	[Redacted]	[Redacted]
[Redacted]	[Redacted]	[Redacted]	[Redacted]	[Redacted]	[Redacted]	[Redacted]

CCI

[REDACTED]	[REDACTED]	[REDACTED]	[REDACTED]	[REDACTED]	[REDACTED]	[REDACTED]
[REDACTED]	[REDACTED]	[REDACTED]	[REDACTED]	[REDACTED]	[REDACTED]	[REDACTED]
[REDACTED]	[REDACTED]	[REDACTED]	[REDACTED]	[REDACTED]	[REDACTED]	[REDACTED]

[REDACTED]	[REDACTED]	[REDACTED]	[REDACTED]	[REDACTED]	[REDACTED]	[REDACTED]
[REDACTED]	[REDACTED]	[REDACTED]	[REDACTED]	[REDACTED]	[REDACTED]	[REDACTED]
[REDACTED]	[REDACTED]	[REDACTED]	[REDACTED]	[REDACTED]	[REDACTED]	[REDACTED]

[REDACTED]	[REDACTED]	[REDACTED]	[REDACTED]	[REDACTED]	[REDACTED]	[REDACTED]
[REDACTED]	[REDACTED]	[REDACTED]	[REDACTED]	[REDACTED]	[REDACTED]	[REDACTED]
[REDACTED]	[REDACTED]	[REDACTED]	[REDACTED]	[REDACTED]	[REDACTED]	[REDACTED]

[REDACTED]	[REDACTED]	[REDACTED]	[REDACTED]	[REDACTED]	[REDACTED]	[REDACTED]
[REDACTED]	[REDACTED]	[REDACTED]	[REDACTED]	[REDACTED]	[REDACTED]	[REDACTED]
[REDACTED]	[REDACTED]	[REDACTED]	[REDACTED]	[REDACTED]	[REDACTED]	[REDACTED]

7.0 CCI [Redacted]

[Redacted]

[Redacted]

[Redacted]	[Redacted]	[Redacted]	[Redacted]	[Redacted]	[Redacted]	[Redacted]	[Redacted]
[Redacted]	[Redacted]	[Redacted]	[Redacted]	[Redacted]	[Redacted]	[Redacted]	[Redacted]
[Redacted]	[Redacted]	[Redacted]	[Redacted]	[Redacted]	[Redacted]	[Redacted]	[Redacted]
[Redacted]	[Redacted]	[Redacted]	[Redacted]	[Redacted]	[Redacted]	[Redacted]	[Redacted]

[Redacted]

[Redacted]	[Redacted]	[Redacted]	[Redacted]	[Redacted]	[Redacted]	[Redacted]	[Redacted]
[Redacted]	[Redacted]	[Redacted]	[Redacted]	[Redacted]	[Redacted]	[Redacted]	[Redacted]
[Redacted]	[Redacted]	[Redacted]	[Redacted]	[Redacted]	[Redacted]	[Redacted]	[Redacted]
[Redacted]	[Redacted]	[Redacted]	[Redacted]	[Redacted]	[Redacted]	[Redacted]	[Redacted]

[Redacted]

[Redacted]	[Redacted]	[Redacted]	[Redacted]	[Redacted]	[Redacted]	[Redacted]	[Redacted]
[Redacted]	[Redacted]	[Redacted]	[Redacted]	[Redacted]	[Redacted]	[Redacted]	[Redacted]
[Redacted]	[Redacted]	[Redacted]	[Redacted]	[Redacted]	[Redacted]	[Redacted]	[Redacted]
[Redacted]	[Redacted]	[Redacted]	[Redacted]	[Redacted]	[Redacted]	[Redacted]	[Redacted]

[Redacted]

[Redacted]	[Redacted]	[Redacted]	[Redacted]	[Redacted]	[Redacted]	[Redacted]	[Redacted]
[Redacted]	[Redacted]	[Redacted]	[Redacted]	[Redacted]	[Redacted]	[Redacted]	[Redacted]
[Redacted]	[Redacted]	[Redacted]	[Redacted]	[Redacted]	[Redacted]	[Redacted]	[Redacted]
[Redacted]	[Redacted]	[Redacted]	[Redacted]	[Redacted]	[Redacted]	[Redacted]	[Redacted]

[Redacted]

[Redacted]	[Redacted]	[Redacted]	[Redacted]	[Redacted]	[Redacted]	[Redacted]	[Redacted]
[Redacted]	[Redacted]	[Redacted]	[Redacted]	[Redacted]	[Redacted]	[Redacted]	[Redacted]
[Redacted]	[Redacted]	[Redacted]	[Redacted]	[Redacted]	[Redacted]	[Redacted]	[Redacted]
[Redacted]	[Redacted]	[Redacted]	[Redacted]	[Redacted]	[Redacted]	[Redacted]	[Redacted]

CCI

[REDACTED]	[REDACTED]	[REDACTED]	[REDACTED]	[REDACTED]	[REDACTED]	[REDACTED]
[REDACTED]	[REDACTED]	[REDACTED]	[REDACTED]	[REDACTED]	[REDACTED]	[REDACTED]
[REDACTED]	[REDACTED]	[REDACTED]	[REDACTED]	[REDACTED]	[REDACTED]	[REDACTED]

[REDACTED]	[REDACTED]	[REDACTED]	[REDACTED]	[REDACTED]	[REDACTED]	[REDACTED]	[REDACTED]
[REDACTED]	[REDACTED]	[REDACTED]	[REDACTED]	[REDACTED]	[REDACTED]	[REDACTED]	[REDACTED]
[REDACTED]	[REDACTED]	[REDACTED]	[REDACTED]	[REDACTED]	[REDACTED]	[REDACTED]	[REDACTED]
[REDACTED]	[REDACTED]	[REDACTED]	[REDACTED]	[REDACTED]	[REDACTED]	[REDACTED]	[REDACTED]
[REDACTED]	[REDACTED]	[REDACTED]	[REDACTED]	[REDACTED]	[REDACTED]	[REDACTED]	[REDACTED]

[REDACTED]	[REDACTED]	[REDACTED]	[REDACTED]	[REDACTED]	[REDACTED]	[REDACTED]
[REDACTED]	[REDACTED]	[REDACTED]	[REDACTED]	[REDACTED]	[REDACTED]	[REDACTED]
[REDACTED]	[REDACTED]	[REDACTED]	[REDACTED]	[REDACTED]	[REDACTED]	[REDACTED]

[REDACTED]	[REDACTED]	[REDACTED]	[REDACTED]	[REDACTED]	[REDACTED]	[REDACTED]
[REDACTED]	[REDACTED]	[REDACTED]	[REDACTED]	[REDACTED]	[REDACTED]	[REDACTED]
[REDACTED]	[REDACTED]	[REDACTED]	[REDACTED]	[REDACTED]	[REDACTED]	[REDACTED]

[REDACTED]	[REDACTED]	[REDACTED]	[REDACTED]	[REDACTED]	[REDACTED]	[REDACTED]
[REDACTED]	[REDACTED]	[REDACTED]	[REDACTED]	[REDACTED]	[REDACTED]	[REDACTED]
[REDACTED]	[REDACTED]	[REDACTED]	[REDACTED]	[REDACTED]	[REDACTED]	[REDACTED]

CCI [Redacted]

[Redacted]

[Redacted]	[Redacted]	[Redacted]	[Redacted]	[Redacted]	[Redacted]	[Redacted]
[Redacted]	[Redacted]	[Redacted]	[Redacted]	[Redacted]	[Redacted]	[Redacted]
[Redacted]	[Redacted]	[Redacted]	[Redacted]	[Redacted]	[Redacted]	[Redacted]
[Redacted]	[Redacted]	[Redacted]	[Redacted]	[Redacted]	[Redacted]	[Redacted]

[Redacted]

[Redacted]

[Redacted]	[Redacted]	[Redacted]	[Redacted]	[Redacted]	[Redacted]	[Redacted]
[Redacted]	[Redacted]	[Redacted]	[Redacted]	[Redacted]	[Redacted]	[Redacted]
[Redacted]	[Redacted]	[Redacted]	[Redacted]	[Redacted]	[Redacted]	[Redacted]
[Redacted]	[Redacted]	[Redacted]	[Redacted]	[Redacted]	[Redacted]	[Redacted]

[Redacted]

[Redacted]

[Redacted]	[Redacted]
[Redacted]	[Redacted]
[Redacted]	[Redacted]
[Redacted]	[Redacted]
[Redacted]	[Redacted]

[Redacted]

[Redacted]	[Redacted]	[Redacted]
[Redacted]	[Redacted]	[Redacted]
[Redacted]	[Redacted]	[Redacted]
[Redacted]	[Redacted]	[Redacted]
[Redacted]	[Redacted]	[Redacted]
[Redacted]	[Redacted]	[Redacted]
[Redacted]	[Redacted]	[Redacted]
[Redacted]	[Redacted]	[Redacted]

CCI

[REDACTED]	[REDACTED]	[REDACTED]	[REDACTED]	[REDACTED]	[REDACTED]	[REDACTED]	[REDACTED]
[REDACTED]	[REDACTED]	[REDACTED]	[REDACTED]	[REDACTED]	[REDACTED]	[REDACTED]	[REDACTED]
[REDACTED]	[REDACTED]	[REDACTED]	[REDACTED]	[REDACTED]	[REDACTED]	[REDACTED]	[REDACTED]
[REDACTED]	[REDACTED]	[REDACTED]	[REDACTED]	[REDACTED]	[REDACTED]	[REDACTED]	[REDACTED]

[REDACTED]

[REDACTED]

[REDACTED]

[REDACTED]	[REDACTED]	[REDACTED]	[REDACTED]	[REDACTED]	[REDACTED]	[REDACTED]
[REDACTED]	[REDACTED]	[REDACTED]	[REDACTED]	[REDACTED]	[REDACTED]	[REDACTED]
[REDACTED]	[REDACTED]	[REDACTED]	[REDACTED]	[REDACTED]	[REDACTED]	[REDACTED]
[REDACTED]	[REDACTED]	[REDACTED]	[REDACTED]	[REDACTED]	[REDACTED]	[REDACTED]

[REDACTED]

[REDACTED]

[REDACTED]	[REDACTED]	[REDACTED]	[REDACTED]	[REDACTED]	[REDACTED]	[REDACTED]
[REDACTED]	[REDACTED]	[REDACTED]	[REDACTED]	[REDACTED]	[REDACTED]	[REDACTED]
[REDACTED]	[REDACTED]	[REDACTED]	[REDACTED]	[REDACTED]	[REDACTED]	[REDACTED]
[REDACTED]	[REDACTED]	[REDACTED]	[REDACTED]	[REDACTED]	[REDACTED]	[REDACTED]

8.0 CCI [Redacted]

[Redacted]

[Redacted]

[Redacted]	[Redacted]
[Redacted]	[Redacted]

[Redacted]

[Redacted]

[Redacted]	[Redacted]	[Redacted]	[Redacted]
[Redacted]	[Redacted]	[Redacted]	[Redacted]

[Redacted]

[Redacted]

[Redacted]

CCI [Redacted]

[Redacted]	[Redacted]	[Redacted]	[Redacted]	[Redacted]	[Redacted]	[Redacted]
[Redacted]						
[Redacted]						
[Redacted]						
[Redacted]						
[Redacted]	[Redacted]	[Redacted]	[Redacted]	[Redacted]	[Redacted]	[Redacted]
[Redacted]						

9.0 CCI [Redacted]

CCI [Redacted]

[Redacted]

[Redacted]

[Redacted]

[Redacted]	[Redacted]	[Redacted]	[Redacted]	[Redacted]	[Redacted]	[Redacted]
[Redacted]	[Redacted]	[Redacted]	[Redacted]	[Redacted]	[Redacted]	[Redacted]
[Redacted]	[Redacted]	[Redacted]	[Redacted]	[Redacted]	[Redacted]	[Redacted]
[Redacted]	[Redacted]	[Redacted]	[Redacted]	[Redacted]	[Redacted]	[Redacted]
[Redacted]	[Redacted]	[Redacted]	[Redacted]	[Redacted]	[Redacted]	[Redacted]
[Redacted]	[Redacted]	[Redacted]	[Redacted]	[Redacted]	[Redacted]	[Redacted]
[Redacted]	[Redacted]	[Redacted]	[Redacted]	[Redacted]	[Redacted]	[Redacted]
[Redacted]	[Redacted]	[Redacted]	[Redacted]	[Redacted]	[Redacted]	[Redacted]
[Redacted]	[Redacted]	[Redacted]	[Redacted]	[Redacted]	[Redacted]	[Redacted]
[Redacted]	[Redacted]	[Redacted]	[Redacted]	[Redacted]	[Redacted]	[Redacted]
[Redacted]	[Redacted]	[Redacted]	[Redacted]	[Redacted]	[Redacted]	[Redacted]
[Redacted]	[Redacted]	[Redacted]	[Redacted]	[Redacted]	[Redacted]	[Redacted]
[Redacted]	[Redacted]	[Redacted]	[Redacted]	[Redacted]	[Redacted]	[Redacted]
[Redacted]	[Redacted]	[Redacted]	[Redacted]	[Redacted]	[Redacted]	[Redacted]
[Redacted]	[Redacted]	[Redacted]	[Redacted]	[Redacted]	[Redacted]	[Redacted]

CCI	[REDACTED]	[REDACTED]	[REDACTED]	[REDACTED]	[REDACTED]	[REDACTED]	[REDACTED]
[REDACTED]	[REDACTED]	[REDACTED]	[REDACTED]	[REDACTED]	[REDACTED]	[REDACTED]	[REDACTED]
[REDACTED]	[REDACTED]	[REDACTED]	[REDACTED]	[REDACTED]	[REDACTED]	[REDACTED]	[REDACTED]

10.0 CCI

11.0 APPENDIX F: Coding tables

Table 1: Mental health ICD diagnosis codes

Condition	ICD-10 dx
Schizophrenia	F20.1x, F20.2x, F20.0x, F21.x, F20.5x, F20.89x, F20.3x, F20.9x
Depression	F32.x, F33.x
Bipolar disorder	F30.9x, F30.10x, F31.0x, F31.1x, F31.2x, F31.3x, F31.4x, F31.5x, F31.6x, F31.9x, F31.8x, F31.7x

Table 2a: Non-LAI atypical antipsychotic GPI Codes

Brand Name	Generic Name	GPI Code
FANAPT	Iloperidone	59070035000310 59070035000320 59070035000340 59070035000360 59070035000380 59070035000385 59070035000390
FANAPT TITRATION PACK	Iloperidone	59070035006320
INVEGA	Paliperidone	59070050007505 59070050007510 59070050007520 59070050007530
PALIPERIDONE ER	Paliperidone	59070050007505 59070050007510 59070050007520 59070050007530
RISPERDAL	Risperidone	59070070000303 59070070000306 59070070000310 59070070000320 59070070000330 59070070000340 59070070002010
RISPERDAL M-TAB	Risperidone	59070070007220 59070070007230 59070070007240 59070070007250 59070070007260
RISPERIDONE	Risperidone	59070070000303 59070070000306 59070070000310 59070070000320 59070070000330 59070070000340 59070070002010
RISPERIDONE M-TAB	Risperidone	59070070007220 59070070007230 59070070007240 59070070007250 59070070007260

RISPERIDONE ODT	Risperidone	59070070007210 59070070007220 59070070007230 59070070007240 59070070007250 59070070007260
QUETIAPINE FUMARATE	Quetiapine Fumarate	59153070100310 59153070100314 59153070100320 59153070100330 59153070100340 59153070100350
QUETIAPINE FUMARATE ER	Quetiapine Fumarate	59153070107505 59153070107515 59153070107520 59153070107530 59153070107540
SEROQUEL	Quetiapine Fumarate	59153070100310 59153070100314 59153070100320 59153070100330 59153070100340 59153070100350
SEROQUEL XR	Quetiapine Fumarate	59153070107505 59153070107515 59153070107520 59153070107530 59153070107540
SAPHRIS	Asenapine Maleate	59155015100710 59155015100720 59155015100730
OLANZAPINE	Olanzapine	59157060000305 59157060000310 59157060000315 59157060000320 59157060000330 59157060000340 59157060002120
OLANZAPINE ODT	Olanzapine	59157060007210 59157060007220 59157060007230 59157060007240

ZYPREXA	Olanzapine	59157060000305 59157060000310 59157060000315 59157060000320 59157060000330 59157060000340 59157060002120
ZYPREXA ZYDIS	Olanzapine	59157060007210 59157060007220 59157060007230 59157060007240
ABILIFY	Aripiprazole	59250015000305 59250015000310 59250015000320 59250015000330 59250015000340 59250015000350 59250015002020 59250015002050
ABILIFY DISCMELT	Aripiprazole	59250015007220 59250015007230
ABILIFY MAINTENA	Aripiprazole	5925001500E430 5925001500E440 5925001500G230 5925001500G240
ARIPIPRAZOLE	Aripiprazole	59250015000305 59250015000310 59250015000320 59250015000330 59250015000340 59250015000350 59250015002020
ARIPIPRAZOLE ODT	Aripiprazole	59250015007220 59250015007230
REXULTI	Brexipiprazole	59250020000310 59250020000320 59250020000330 59250020000340 59250020000350 59250020000360
VRAYLAR	Cariprazine HCl	59400018100120 59400018100130

		59400018100140 59400018100150 5940001810B220
LATUDA	Lurasidone HCl	59400023100310 59400023100320 59400023100330 59400023100340 59400023100350
NUPLAZID	Pimavanserin Tartrate	59400028200320
GEODON	Ziprasidone HCl	59400085100120 59400085100130 59400085100140 59400085100150
ZIPRASIDONE HCL	Ziprasidone HCl	59400085100120 59400085100130 59400085100140 59400085100150
GEODON	Ziprasidone Mesylate	59400085202120

Table 2b: LAI atypical antipsychotic GPI Codes

Brand Name	Generic Name	GPI Code
INVEGA SUSTENNA	Paliperidone Palmitate	59070050101837 59070050101838 59070050101839 59070050101840 59070050101845
INVEGA TRINZA	Paliperidone Palmitate	59070050101850 59070050101860 59070050101870 59070050101880
RISPERDAL CONSTA	Risperidone Microspheres	59070070101910 59070070101920 59070070101930 59070070101940
ZYPREXA RELPREVV	Olanzapine Pamoate	59157060101950 59157060101960 59157060101970
ABILIFY MAINTENA	Aripiprazole	59250015001920 59250015001930
ARISTADA	Aripiprazole Lauroxil	5925001520E420 5925001520E430 5925001520E440 5925001520E450

This page is a manifestation of an electronically captured signature

SIGNATURE PAGE

Document Name: P31613217 Statistical Analysis PLaN

Document Number: 1000055470

Document Version: 3.0

Signed by	Meaning of Signature	Server Date (dd-MMM- yyyy hh:min) - UTC timezone
PPD	Biostatistics Approval	14-Oct-2019 21:18:24
PPD	Clinical Approval	14-Oct-2019 19:01:03

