3.4 Virtual Matched Control Group

Enrolled patients will be matched to a virtual control group in a 1:3 ratio (enrolled patients on Abilify MyCite treatment : virtual matched controls). [REDACTED]

The matching process will be conducted after 6-month study data (or early termination data, if applicable) is collected for all Abilify MyCite patients. The virtual matched control group identified in this process will be used for all study analyses with a small amount of attrition expected for the 12-month analyses for controls who no longer have Anthem insurance coverage.

A pool of potential controls will first be identified using the following criteria:

- ≥ 1 day of enrollment in an Anthem-affiliated commercial, Medicaid, or Medicare health plan with medical and pharmacy benefits during the observation period (from date of First Patient In up until date of Last Patient In)¹³.
- ≥ 1 pharmacy claim for any atypical antipsychotic (excluding Abilify MyCite, clozapine, and long-acting injectable antipsychotics [LAIs]^{14,15}) during the observation period (Appendix F, Tables 2a and 2b).

¹³ Timeframe may be extended if additional samples are needed.

¹⁴ LAIs include: Aripiprazole monohydrate (Abilify Mantenna), Aripiprazole lauroxil (Aristada), Olanzapine pamoate (Zyprexa Relprevv), Paliperidone palmitate (Invega Sustenna), Paliperidone palmitate (Invega Tri state), Risperidone microspheres (Risperdal Consta)

¹⁵ Drugs include: Aripiprazole, Asenapine, Brexpiprazole, Cariprazine, Iloperidone, Paliperidone, Pimavanserin tartrate, Quetiapine fumarate, Risperidone, Ziprasidone, Ziprasidone Mesylate

- ≥ 1 all-cause hospitalization or partial psychiatric hospitalization¹⁶ that occurs at most 60 days prior to a pharmacy claim for any atypical antipsychotic (excluding Abilify MyCite, clozapine, and LAIs).
 - The earliest such pharmacy claim observed after the earliest observed hospitalization will be set as the initial (temporary) index date for each potential control.
 - For patients with ≥ 2 qualifying hospitalization/pharmacy claim episodes, an iterative process will be used to find the best match, and the final index date will be assigned accordingly.
- Age 18 to 63 on index date.
- ≥ 1 claim for SCH, BP1, or MDD on or before index date.
- No claims for pregnancy during the observation period.
- No claims for any LAI during the observation period.
- ≥ 180 days of medical and pharmacy enrollment prior to index date

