5.0 STATISTICAL ANALYSES

The study was earlier terminated after two subjects have enrolled and treated in the study; no efficacy assessment was obtained for these two subjects. Thus, only patient baseline information of the two subjects is summarized.

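### Appendix F of the SAP lists four Abilify Maintena codes as non-LAI and omits them from the LAI table, so a control pool built from the tables could admit people SAP 3.4 excludes

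*SAP*

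**What the plan says.** SAP 3.4 builds the pool of virtual controls from claims. Four of its elements matter here.

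- **Qualifying claim.** A potential control needs a pharmacy claim for an atypical antipsychotic other than Abilify MyCite, clozapine or an LAI. The codes are given by reference: "during the observation period (Appendix F, Tables 2a and 2b".
- **Definition of an LAI.** Footnote 14 begins "LAIs include: Aripiprazole monohydrate (Abilify Mantenna", so Maintena (misspelled) is the first product named.
- **LAI exclusion.** A separate criterion reads "No claims for any LAI during the observation period".
- **Index date.** "The earliest such pharmacy claim observed after the earliest observed hospitalization will be set as the initial (temporary) index date". A qualifying claim can therefore start a control's follow-up.

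Appendix F then supplies the codes. Under the heading "Table 2a: Non-LAI atypical antipsychotic GPI Codes" there is an Abilify Maintena row with "5925001500E430 5925001500E440 5925001500G230 5925001500G240". Table 2b, for LAIs, also has an Abilify Maintena row, but it holds only "59250015001920 59250015001930".

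On the enrolled side, exclusion criterion 3 in protocol Table 3.3.5-1 keeps out patients currently treated with an LAI antipsychotic.

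**The concern.** The same brand is classed as LAI in one table and as non-LAI in the other, under different codes. Only one of these agrees with footnote 14. A programmer who takes Table 2a as the list of qualifying drugs and Table 2b as the list of excluded drugs would apply a different rule from the one in the text.

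The virtual controls are the only comparator for the primary endpoint. Their membership, their index dates and their exclusions all depend on these claim rules. One misplaced row therefore acts in three places: it can bring a person in, set that person's time zero, and stop the exclusion from removing them. Enrolled patients on an LAI are kept out by the protocol, so the two cohorts would be selected by different rules on this point.

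**Working it through.** The plan gives no figure to reproduce. The check compares two code lists with each other and with the text.

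**Inputs.** All codes printed in SAP Appendix F, Tables 2a and 2b; the control-pool criteria and footnotes 14 and 15 in SAP 3.4.

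**Step 1: count the lists.** Codes repeated across brand and generic rows are counted once.

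- Table 2a has 30 rows. Distinct codes by drug: iloperidone 8, paliperidone 4, risperidone 13, quetiapine 11, asenapine 3, olanzapine 11, aripiprazole 14, brexpiprazole 6, cariprazine 5, lurasidone 5, pimavanserin 1, ziprasidone 5. Sum: 8 + 4 + 13 + 11 + 3 + 11 + 14 + 6 + 5 + 5 + 1 + 5 = 86.
- Table 2b has 6 rows: 5 + 4 + 4 + 3 + 2 + 4 = 22 distinct codes.
- Codes common to both tables: 0.

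**Step 2: locate the Maintena codes.**

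| | Table 2a (non-LAI) | Table 2b (LAI) | Total |
|---|---|---|---|
| As printed | 4 | 2 | 6 |
| As footnote 14 implies | 0 | 6 | 6 |

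Share in the wrong table: 4/6 = 67%. After correction, Table 2a holds 86 − 4 = 82 codes and Table 2b holds 22 + 4 = 26. Share of the corrected LAI list now missing from the exclusion: 4/26 = 15%. These are shares of code strings, not of claims or people.

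**Step 3: trace one person through the rules.** Take someone hospitalized within the previous 60 days whose only LAI claims carry the four codes, and apply the tables literally.

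1. Qualifying claim: the code is in Table 2a, so the claim counts.
2. Index date: if it is the earliest such claim after the hospitalization, it becomes the temporary index date.
3. LAI exclusion: the code is not in Table 2b, so nothing is flagged.

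If the remaining criteria are met, the person enters the pool, although SAP 3.4 says they should not. Someone who also has a claim under any Table 2b code is still removed at item 3.

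**Step 4: is the row an extraction fault?** This is unlikely. The row has its own brand and generic name, sits in code order between Abilify Discmelt and generic aripiprazole, and is followed by nine more Table 2a rows before Table 2b starts.

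**Step 5: would a shorter code match repair it?** No. All six Maintena codes begin 5925001500. So do the ten other aripiprazole codes in Table 2a (eight under Abilify, two under Discmelt, with the generic rows repeating codes from these). Excluding on that ten-character stem would remove 6 + 10 = 16 codes, including ten that the plan accepts as qualifying.

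**The case against.** The strongest reply is that the text governs and is clear. Footnote 14 names the product, the LAI exclusion cites no table, and the stray row carries the brand name, so a careful programmer excluding by name would catch it. That is fair, and it makes the effect conditional. It is not a dependable safeguard, however. Footnote 14 spells the brand differently from the tables and gives the ingredient as the monohydrate, whereas both Maintena rows say only aripiprazole. An exact name match would fail on either field. Footnote 15 lists aripiprazole among the eligible drugs, so a filter on generic name would let the row through.

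A second reply is that the study ended after two subjects and, in the words of SAP 5.0, "no efficacy assessment was obtained for these two subjects". This stands: no reported comparison was affected. Even so, the current SAP keeps both the control-pool rules and Appendix F as plan text.

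Third, the percentages count codes, and the four codes might carry many claims or none. This also stands, and no direction of bias can be given.

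Fourth, the documents contain no drug dictionary, so the brand label on that row could be the error rather than its placement. This seems less likely, but it is a reason to verify the codes before moving them. Likewise, SAP 3.4 dates the index from a pharmacy claim, and the documents do not say that this is the day of injection.

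**Conclusion.** The contradiction is real and visible on the page. Four of the six Maintena codes in Appendix F are in the table that SAP 3.4's own definition rules out, and the LAI table is four codes short of 26. Applied literally, the tables would admit some LAI users to the only comparator group and could start their follow-up at an LAI claim.

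This rests on two assumptions: that the brand label on the row is correct, and that the pool is programmed from the tables without a working name-based check. The number of controls affected cannot be calculated, because the documents give no claim counts by code. With the study stopped, the defect lies in the plan and in any use of this code list, not in a result. It should be corrected.

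**What to change.** Confirm the four codes against the drug dictionary as a routine check, then move them from Table 2a to Table 2b. Table 2a then has 82 distinct codes and Table 2b has 26, six of them for Maintena. State that matching uses the full 14-character code, because the first ten characters do not separate Maintena from the other aripiprazole codes. Apply the qualifying-claim rule, the index-date rule and the LAI exclusion with the corrected lists. Correcting the brand spelling in footnote 14 at the same time would let names and codes be cross-checked.

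The cost is an edit to one SAP appendix. It needs no new data and leaves the rule in SAP 3.4 unchanged.
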